1. Visit 1 of this LT extension study should preferably be performed in one visit combined with the last visit of the preceding trial 1311.6 or during the interim period of maximum 5 days after completion of the last visit in 1311.6. If an EoT colonoscopy has not been performed during E1 within 1311.6, it must be performed between V1 and V2 in 1311.20/M15-989.
2. Assessments performed at the last visit in the previous trial do not have to be repeated at visit 1 in this trial. Assessments scheduled but not performed at the last visit in the previous trial should be repeated at Visit 1 in this trial, and the results entered into the CRFs of both trials 1311.6 and 1311.20/M15-989.
3. For patients who discontinue study medication before scheduled EoT visit, an early EoT visit should be performed. After last dose of study medication, a 140 day follow-up call should be scheduled. Upon EC/CA approvals of Study M16-000 protocol amendment 4, patients receiving treatment in M15-989 will have the option to enroll into M16-000 Sub-Study 3 after completing the EoT visit.
4. Must be performed at Visit 1 and starting from Visit 2 prior to each study drug administration in females of childbearing potential. In case of positive result, serum pregnancy test will be performed. Study drug will only be administered if pregnancy is ruled out.
5. Positive QuantiFERON-TB Gold In-Tube tests need not to be repeated. If TB or infection is suspected at any time during the study, a routine work up including chest x-ray and a QuantiFERON-TB Gold In-Tube test or an infection assessment must be performed at investigator's discretion and according to local guidelines.
6. Assessment of AE after subcutaneous injections will also include assessment of local tolerability. The assessment of local tolerability should be done just before the patient leaves the investigator site.
7. All assessments are to be completed prior to study drug administration, unless otherwise specified.
8. An end of trial call should be performed for both patients that agree to enroll into M16-000 Sub-Study 3 OLE or those that do not choose to participate.
9. For details of laboratory tests see [Section 5.2.3](#), [Table 5.2.3:1](#) and [Table 5.2.3:2](#).

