Administration of trial s.c. medication ⁷	X	X	X	X	X	X	X	X	X	X	X

1. If an EoT colonoscopy has not been performed during E1/E5 within 1311.6, or if the patient had a treatment interruption followed by a clinical relapse, it must be performed between V1 and V2 in 1311.20/M15-989.
2. Assessments performed at visit E1/E5 in the previous trial do not have to be repeated at Visit 1 in this trial. Assessments scheduled but not performed at Visit E1/E5 in the previous trial should be repeated at visit 1 in this trial, and the results entered into the CRFs of both trials, 1311.6 and 1311.20/M15-989.
3. For patients who discontinue study medication before scheduled EoT visit, an early EoT visit should be performed. After last dose of study medication, a 140 day follow-up call should be scheduled. Upon EC/CA approvals of Study M16-000 protocol amendment 4, patients receiving treatment in M15-989 will have the option to enroll into M16-000 Sub-Study 3 after completing the EoT visit.
4. Must be performed at Visit 1 and starting from Visit 2 prior to each study drug administration in females of childbearing potential. In case of positive result, serum pregnancy test will be performed. Study drug will only be administered if pregnancy is ruled out.
5. Positive QuantiFERON-TB Gold In-Tube tests need not to be repeated. If TB or infection is suspected at any time during the study, a routine work up including chest x-ray and a QuantiFERON-TB Gold In-Tube test or an infection assessment must be performed at investigator's discretion and according to local guidelines.
6. Assessment of AE after intravenous infusions and subcutaneous injections will also include assessment of local tolerability. The assessment of local tolerability should be done just before the patient leaves the investigator site.
7. All assessments are to be completed prior to study drug administration, unless otherwise specified.
8. An end of trial call should be performed for both patients that agree to enroll into M16-000 Sub-Study 3 OLE or those that do not choose to participate.
9. For details of laboratory tests see [Section 5.2.3](#), [Table 5.2.3.1](#) and [Table 5.2.3.2](#).
10. Every effort should be made for the patient to perform a final ileocolonoscopy at the study visit where the last dose of study medication is administered. For patients with early EoT, every effort should be made to perform a final ileocolonoscopy within 2 weeks following the early EoT visit.

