- If clinical remission (achieved at E5 1311.6) has been lost after end of treatment in 1311.6 and/or at screening for 1311.20/M15-989, patients will receive open label i.v. re-induction treatment with three infusions of 600 mg each every 4 weeks after which eligibility will be re-assessed. If clinical remission or at least response compared to 1311.6 study baseline (V2) is achieved patients will switch to s.c. maintenance treatment with 180 mg s.c. every 8 weeks ([Flow chart 3](#)), otherwise an EoT visit has to be performed. After last administration of trial drug in 1311.20/M15-989 trial, a 140 day follow up call should be scheduled for patients who do not elect to enroll in Study M16-000.
- If clinical response (achieved at E1 or E5 1311.6) has been lost after end of treatment in 1311.6 and/or at screening for 1311.20/M15-989, patients will receive open label i.v. re-induction treatment with three infusions of 600 mg each every 4 weeks after which eligibility will be re-assessed. If clinical response or remission compared to 1311.6 study baseline (V2 1311.6) is achieved patients will switch to s.c. maintenance treatment with 180 mg s.c. every 8 weeks ([Flow chart 3](#)), otherwise an EoT visit has to be performed. After last administration of trial drug in 1311.20/M15-989 trial, a 140 day follow up call should be scheduled for patients who do not elect to enroll in Study M16-000.

The results from the last colonoscopy done in 1311.6 will serve as baseline for 1311.20/M15-989. A colonoscopy at screening is only required for patients who lost

response or remission during extended follow-up phase after completion of 1311.6. Colonoscopies are repeated once per year to assess the effect of continued treatment on endoscopic response and mucosal healing.

The end of study is defined as the date the last subject completes the End of trial visit

The primary analysis will be performed after all patients have completed their EoT visit. The reference values for the efficacy endpoints clinical or endoscopic response will be the baseline values in 1311.6.

For details regarding Adverse event and serious adverse event reporting, see [Section 5.2.2.2](#)

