7.2 NULL AND ALTERNATIVE HYPOTHESES

There is no formal statistical hypothesis test planned.

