4.2 Study Design

This open label long term extension trial investigates the long-term safety and efficacy of BI 655066/ABBV-066 (risankizumab). Approximately 60 patients who met the entry criteria were planned for inclusion in this trial, rolling over from preceding trial Study M15-993/1311.6.

[figure not shown]
All patients directly rolled over from Study M15-993/1311.6 into Study M15-989/1311.20 received 180 mg BI 655066/ABBV-066 (risankizumab) subcutaneously (SC) from Visit 2 onwards every 8 weeks. Patients who lost clinical response or remission after the end of treatment in Study M15-993/1311.6 and/or at screening for Study 1311.20/M15-989 received open label, i.e., re-induction treatment with three intravenous infusions (IV) of 600 mg each every 4 weeks. Patients who complete this study may elect to continue in Study M16-000 Sub-Study 3 (Phase 3 open label extension study).

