6.4 Definition of Visit Windows

Since subjects do not always adhere to the study visit schedule, the following rules will be applied to assign actual visits to protocol-specified visits including early termination visits. For each study visit mentioned in the protocol, a nominal or target day will be selected to represent the corresponding visit along with a window around the target day. Windows will be selected in a non-overlapping fashion so that a date collected on the case

report form (CRF) does not correspond to multiple visit windows. Moreover, windows will not discard any post-baseline measurement recorded on the CRF. If a subject had 2 or more actual visits in one visit window, the visit closest to the target will be used as the study visit for that window. If two visits are equidistant from the target day, then the later visit will be used for reporting.

The visit windows and the target/nominal day for each study visit are shown in the tables below. The visit windows defined below will be based on relative days to either first dose on IV or first dose on SC.

Table 1. Windows for subcutaneous injection period for ITT_SC (SA_SC) population, using for Vital sign, Lab Values, Fistula exam, CDAI, Review patient diary (PRO data).

Nominal Visit Week^d	Lower Bound	Nominal Day	Upper Bound
0	-999	1 ^a	1
8	2	57	85
X ^c	$1 + 7*(X - 4) + 1$	$1 + 7*X$	$1 + 7*(X + 4)$
200	1374	1401	9999 ^b

- a. Day of first dose of study drug for subcutaneous injection.
- b. It is minimum of (the last dose date + 140 days, the first dose date of Study M16-000 sub-Study 3) for the subjects who entered the Study M16-000 sub-Study 3; otherwise it is the last dose date +140 days.
- c. $X = 8*i$, $i = 2, \dots, 24$.
- d. Nominal visit week is a transformation of the protocol-specified week. For the patients' schedule following the Flow Chart 1, nominal visit week = protocol-specified week – 4. For the patients' schedule following the Flow Chart 2, nominal visit week = protocol-specified week – 6. For the patients' schedule following the Flow Chart 3 (only for subcutaneous injection period), nominal visit week = protocol-specified week – 16.

Table 2. Windows for subcutaneous injection period for ITT_SC population, using for CDEIS and SES-CD.

Nominal Visit Week ^c	Lower Bound	Nominal Day	Upper Bound
0	-999	1 ^a	1
48	2	337	533
104	534	729	897
152	898	1065	1233
200	1234	1401	9999 ^b

- a. Day of first dose of study drug for subcutaneous injection.

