- d. Nominal visit week is a transformation of the protocol-specified week. For the patients' schedule following the Flow Chart 1, nominal visit week = protocol-specified week - 4. For the patients' schedule following the Flow Chart 2, nominal visit week = protocol-specified week - 6. For the patients' schedule following the Flow Chart 3 (only for subcutaneous injection period), nominal visit week = protocol-specified week - 16.
- e. Since some fecal calprotectin data at screening visit are loaded into the last visit of the feeder Study M15-993, the combined fecal calprotectin data from the feeder Study M15-993 and the current Study M15-989 will be used to derive the value at Week 0.

Table 5. Windows for subcutaneous injection period for ITT_SC population, using for hs-CRP.

Nominal Visit Week ^d	Lower Bound	Nominal Day	Upper Bound
0	-999 ^e	1 ^a	1
8	2	57	113
X ^c	1 + 7*(X - 8) + 1	1 + 7*X	1 + 7*(X + 8)
120	786	841	869
128	870	897	925
136	926	953	985
152	986	1065	1093
160	1094	1121	1177
176	1178	1233	1261
184	1262	1289	1345
200	1346	1401	9999 ^b

- a. Day of first dose of study drug for subcutaneous injection.
- b. It is minimum of (the last dose date + 140 days, the first dose date of Study M16-000 sub-Study 3) for the subjects who entered the Study M16-000 sub-Study 3; otherwise it is the last dose date + 140 days.
- c. $X = 8 + 16*i$, $i = 1, 2, 3, 4, 5, 6$.
- d. Nominal visit week is a transformation of the protocol-specified week. For the patients' schedule following the Flow Chart 1, nominal visit week = protocol-specified week - 4. For the patients' schedule following the Flow Chart 2, nominal visit week = protocol-specified week - 6. For the patients' schedule following the Flow Chart 3 (only for subcutaneous injection period), nominal visit week = protocol-specified week - 16.
- e. Since some hs-CRP data at screening visit are loaded into the last visit of the feeder Study M15-993, the combined hs-CRP data from the feeder Study M15-993 and the current Study M15-989 will be used to derive the value at Week 0.

Table 6. Windows for IV injection period for ITT_IV (SA_IV) population, using for Vital sign Lab Values, Fistula exam, CDAI, Review patient diary (PRO data)

Nominal Visit Week ^b	Lower Bound	Nominal Day	Upper Bound
0	-999	1 ^a	1
4	2	29	43
8	44	57	71

- a. Day of first dose of study drug for IV injection.

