12.9 Analysis Convention for Composite Endpoints

The value of composite endpoints, such as deep remission, is decided by the value of each component at the visits with planned measurements for all components. In details, taking deep remission as an example, one of its components, clinical remission, is measured every eight weeks, i.e., Week 0, 8, 16, 24 etc. The other component, CDEIS remission, is measured every year, i.e., Week 0, Week 48, Week 104, Week 152, Week 200. Hence the observed value of deep remission will be evaluated at Week 0, Week 48, Week 104,

Week 152, Week 200 based on the value of each component endpoint at the corresponding visit, according to [Table 11](#) below, where, for deep remission, the endpoint A = Clinical remission, the endpoint B = CDEIS remission.

Table 11. How to calculate the observed value of endpoint C = A and B for different scenarios

Scenarios	A at Week X*	B at Week X*	C at Week X*
Scenario 1	1	1	1
Scenario 2/3/4	1/0/0	0/1/0	0/0/0
Scenario 5/6	1/Missing	Missing/1	Missing/Missing
Scenario 7/8	0/Missing	Missing/0	0
Scenario 9	Missing	Missing	Missing

* X = The visits with both measurements A and B planned. It will be 0, 48, 104, 152, 200 for deep remission.

The other endpoints which have multiple components, i.e., "A and B and C...," such as "Proportion of subjects with average daily SF ≤ 2.8 and not worse than baseline and average daily AP score ≤ 1 and not worse than baseline," could follow the similar logic.

For endpoints with the structure of "A or B," such as "Proportion of subjects with $\geq 60\%$ decrease in average daily SF and/or $\geq 35\%$ decrease in average daily AP score and both not worse than baseline, and/or achievement of average daily SF ≤ 2.8 and AP ≤ 1 and both not worse than baseline," the observed value of such endpoint "C = A or B" can be determined following the logic displayed in [Table 12](#) below.

Table 12. How to calculate the observed value of endpoint C = A or B for different scenarios.

Scenarios	A at Week X*	B at Week X*	C at Week X*
Scenario 1	0	0	0
Scenario 2/3/4	1/0/1	1/1/0	1/1/1
Scenario 5/6	1/Missing	Missing/1	1/1
Scenario 7/8	0/Missing	Missing/0	Missing/Missing
Scenario 9	Missing	Missing	Missing

* X = The visits with both measurements A and B planned.

Document Approval

Study M15989 - Statistical Analysis Plan Version 1 - 15Jul2019 (E3 16.1.9)

Version: 1.0

Date: 17-Jul-2019 03:46:15 AM

Company ID: 07172019-00F9F6842AA885-00001-en

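### SAP Table 2 and 12.9 give re-induced patients an invalid s.c. Week 0 endoscopy and deep-remission value, and leave the source of that value unstated for direct roll-overs

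*SAP*

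**What the plan says.** SAP 6.4 windows the endoscopic scores in the table headed "Table 2. Windows for subcutaneous injection period for ITT_SC population, using for CDEIS and SES-CD". Its Week 0 row runs from Day -999 to Day 1, where Day 1 is the first s.c. dose. The footnotes cover Day 1, the upper limit of the last window and the conversion of protocol weeks; none names a data source. Within a window, the visit closest to the target day is used.

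Tables 4 and 5 have the same Week 0 row plus a footnote e. For calprotectin it states that "the combined fecal calprotectin data from the feeder Study M15-993 and the current Study M15-989 will be used to derive the value at Week 0", and hs-CRP has the matching sentence. Both explain that some screening results were loaded into the last feeder visit.

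On the scopes themselves, the protocol says:
- Flow Charts 1 and 2, footnote 2: "Assessments performed at the last visit in the previous trial do not have to be repeated at visit 1 in this trial".
- Section 3.1: "The results from the last colonoscopy done in 1311.6 will serve as baseline for 1311.20/M15-989". A screening scope is required only for patients who lost response or remission.
- Flow Chart 3, footnote 1, if the E1/E5 scope was not done: "or if the patient had a treatment interruption followed by a clinical relapse, it must be performed between V1 and V2 in 1311.20/M15-989".

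SAP 12.9 states: "Hence the observed value of deep remission will be evaluated at Week 0, Week 48, Week 104", and continues to Weeks 152 and 200. SAP 9.1.2 counts every missing binary value as not achieved, with no exemption for Week 0. SAP 9.3 reports both observed-case and NRI results by visit. SAP 6.1 sets the efficacy baseline at the last value before the first dose in the feeder study, which is a different time point from Week 0.

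**The concern.** Week 0 is the only row that shows endoscopic status at the start of s.c. maintenance, so it should describe patients as they stood then.

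For re-induced patients it cannot. The scope documents the relapse that led to re-induction, while the CDAI at the same nominal visit is taken after re-induction, in patients who must by then have regained response or remission to go on to s.c. treatment (protocol 3.1). Week 0 deep remission therefore combines two disease states separated by three infusions. Reading Week 48 against it would credit any infusion effect to maintenance.

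For direct roll-overs the question is whether the value reaches the analysis at all. An E1 or E5 scope is a feeder-study assessment and need not be repeated. At entry, calprotectin, CRP and colonoscopy are scheduled at Visit 1 and not at Visit 2. The first two have a written feeder-data rule; colonoscopy does not.

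**Working it through.** **1. Table 2 as printed.** Nominal day = 1 + 7 × week: 1 + 7×48 = 337, 1 + 7×104 = 729, 1 + 7×152 = 1065, 1 + 7×200 = 1401. Upper bounds are midpoints: (337+729)/2 = 533, (729+1065)/2 = 897, (1065+1401)/2 = 1233. All seven printed figures agree, so the arithmetic of the table is sound.

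**2. Re-induced patients.** Flow Chart 3 gives V1 at Week 0, infusions at Weeks 4, 8 and 12 (V2 to V4) and the first s.c. dose at Week 16 (V5). Day relative to the first s.c. dose = 7 × (protocol week − 16):
- scope between V1 and V2: 7×(0−16) = -112 to 7×(4−16) = -84;
- infusions: -84, -56, -28;
- CDAI at V5: Day 1, before dosing.

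The scope lies inside -999 to 1. No colonoscopy is scheduled between V2 and V5, so it is the closest to target and becomes s.c. Week 0. Adding feeder data would not change this, because an E1/E5 scope is older still. Table 6, the i.v.-period windows, has no endoscopy row. SAP 12.9 says composites are evaluated where all components have planned measurements; at V5 no scope is planned.

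**3. Direct roll-overs, where the feeder scope would fall.** With Visit 1 combined with the last feeder visit, E1 is 4 weeks before the first s.c. dose (Flow Chart 1, nominally Day -28) and E5 is 6 weeks before (Flow Chart 2, Day -42). Both lie inside the window. For patients who finished 1311.6 before this study opened and kept their response, the scope is older by a gap that the documents do not give.

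**4. Direct roll-overs, if only M15-989 data are used.** CDEIS at Week 0 is missing for everyone scoped only in the feeder study.
- CDEIS remission under NRI: not achieved for all of them.
- Deep remission, observed case (Table 11): CDAI remission with missing CDEIS gives missing; no CDAI remission with missing CDEIS gives 0. A value of 1 cannot occur.
- Deep remission under NRI: the missing values also become failures.

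Illustration with assumed inputs: 60 such patients, 40% to 60% in CDAI remission, 30% to 50% of those in CDEIS remission. True deep remission is 0.40×0.30 = 12% to 0.60×0.50 = 30%. The reported result is 0/36 to 0/24 observed-case (60×0.60 and 60×0.40) and 0/60 under NRI.

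**5. How far the CDEIS row could move.** Let r be the re-induced share, p the entry remission rate in direct roll-overs and q the rate at the pre-re-induction scope. With feeder scopes the row is (1−r)p + rq; without them NRI gives rq. The gap is (1−r)p. None of these inputs is in the documents. Assuming r = 10% to 40% and p = 30% to 50%, the gap is 0.60×0.30 = 18 to 0.90×0.50 = 45 points. This shows sensitivity to the inputs and is not an estimate.

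**The case against.** For direct roll-overs the plan is silent rather than wrong. The -999 bound admits the E1/E5 scope, the closest-visit rule would pick it, protocol 3.1 names it as this study's baseline, and the SAP says it elaborates the protocol. Feeder endoscopy must be loaded anyway for change from baseline. Footnote e records where certain laboratory results were filed; its absence elsewhere does not bar feeder data. The documents do not describe the endoscopy database. All of this stands, so the direct roll-over part is conditional.

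A reader might also infer that later visits will look like improvement, by an 18 to 45 point margin or something like it. The documents do not support that. No endpoint is defined as change from Week 0; protocol 3.1 takes the reference for response from the 1311.6 baseline; and "There is no formal statistical hypothesis test planned". The margin would arise only if feeder scopes were left out, NRI were applied to Week 0, and someone then compared the rows. In addition, E1 roll-overs enter without clinical remission, so their Week 0 deep remission would be low in any case.

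On re-induced patients, the reply is that no better s.c. Week 0 scope exists and that carrying the last value forward is a usual convention. The first half is true and makes the remedy one of labelling. The second does not rescue a value that precedes the whole re-induction course and is then joined to a CDAI that follows it.

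**Conclusion.** For Flow Chart 3 patients the defect follows from the stated rules: the s.c. Week 0 endoscopy and deep-remission values describe the wrong time point, nominally by 84 to 112 days (visit windows shift this by some days) and three infusions. For direct roll-overs the source of the Week 0 value is unspecified. It would be wrong only if M15-989 data alone were used, and then deep remission would be 0 or missing by construction.

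The reach is narrow: the descriptive Week 0 row and any informal reading of later visits against it. Change from the feeder baseline and the rates at Weeks 48 to 200 do not use the Week 0 value and are unaffected. The size cannot be computed. The SAP gives only the planned total ("Approximately 60 patients who met the entry criteria were planned for inclusion in this trial"), with no split between direct roll-overs and re-induced patients and no entry remission rates. The change is still worth making, because it corrects a reported row at little cost.

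**What to change.** In the SAP:
1. Add a footnote to Table 2, modelled on footnote e: for direct roll-overs, Week 0 CDEIS, SES-CD and ulceration come from combined M15-993 and M15-989 data, using the last colonoscopy before the first s.c. dose.
2. For Flow Chart 3 patients, report the V1 to V2 scope as pre-re-induction, and set s.c. Week 0 endoscopic and deep-remission values to not assessed. Say so in 12.9.
3. State in 9.1.2 that NRI does not apply to Week 0.
4. Reconcile the use of baseline in protocol 3.1 (last 1311.6 colonoscopy) with SAP 6.1 (last value before the first feeder dose), for example by calling the former the extension-entry value.

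The cost is wording and one merge of existing feeder data, with no new procedures. The downside is that re-induced patients have no s.c. Week 0 endoscopy row, so its denominator is smaller than ITT_SC and should be printed with it.

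### SAP Table 5 ends the hs-CRP Week 136 window at day 985 instead of day 1009, so values on days 986–1008 go to Week 152 although they lie nearer Week 136

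*SAP*

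**What the plan says.** SAP Section 6.4 assigns actual visits, including early termination visits, to nominal weeks. The principle is that "a nominal or target day will be selected to represent the corresponding visit along with a window around the target day". Windows must not overlap, and no post-baseline measurement may fall outside them. If several visits fall in one window, the one nearest the target day is used.

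Table 5 gives the hs-CRP windows for the subcutaneous period. The columns are nominal week, lower bound, nominal day and upper bound. The two rows at issue are:

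- Week 136: "136 926 953 985"
- Week 152: "152 986 1065 1093"

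Three rows of the same table serve as comparison:

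- Week 128, with the next target 8 weeks later: "128 870 897 925"
- Week 160, with the next target 16 weeks later: "160 1094 1121 1177"
- Week 184, with the next target 16 weeks later: "184 1262 1289 1345"

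Change from baseline in hs-CRP by visit is a secondary efficacy endpoint (SAP Section 4.3.2). It is continuous, and SAP Section 9.1.2 restricts imputation to categorical efficacy variables. Window assignment therefore decides directly which values enter each visit's summary.

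**The concern.** The cut between Week 136 and Week 152 does not lie halfway between the targets. It is 32 days after the first and 80 days before the second. As printed, the Week 152 window reaches 79 days before its target (1065 − 986) and only 28 days after it (1093 − 1065).

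Two kinds of sample can land in the affected stretch.

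- **EoT samples.** The EoT visit includes CRP in all three flow charts and has no fixed week since Protocol Amendment 4. An EoT value on day 1000, for example, is shown as a Week 152 result for a patient who left before Week 152.
- **Late Week 136 samples.** A sample delayed past day 985 leaves Week 136 empty. It is then labelled Week 152, or is used at neither visit if a sample nearer day 1065 exists.

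Protocol Table 5.2.3:1 also lists hsCRP in the routine laboratory panel, which is scheduled at every treatment visit. If those results feed the hs-CRP dataset (the documents do not say), ordinary nominal Week 144 draws (day 1009 ± 7) straddle this range too.

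**Working it through.** **Inputs.** All bounds and targets come from SAP Section 6.4, Tables 1–6. The visit tolerance of ±7 days comes from the flow charts.

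**Step 1: target days.** Nominal day = 1 + 7 × week.

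- Week 136: 1 + 7 × 136 = 953
- Week 152: 1 + 7 × 152 = 1065

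Both agree with Table 5, so the targets are right and only the cut is in question.

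**Step 2: try to reproduce the boundaries.** The rule that fits the tables is: upper bound = (this target + next target) / 2, and next lower bound = upper bound + 1. The midpoint day therefore belongs to the earlier window.

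| Adjacent weeks | Targets | Midpoint | Table 5 upper bound |
|---|---|---|---|
| 8 / 24 | 57, 169 | 113 | 113 |
| 24 / 40 | 169, 281 | 225 | 225 |
| 40 / 56 | 281, 393 | 337 | 337 |
| 56 / 72 | 393, 505 | 449 | 449 |
| 72 / 88 | 505, 617 | 561 | 561 |
| 88 / 104 | 617, 729 | 673 | 673 |
| 104 / 120 | 729, 841 | 785 | 785 |
| 120 / 128 | 841, 897 | 869 | 869 |
| 128 / 136 | 897, 953 | 925 | 925 |
| **136 / 152** | **953, 1065** | **1009** | **985** |
| 152 / 160 | 1065, 1121 | 1093 | 1093 |
| 160 / 176 | 1121, 1233 | 1177 | 1177 |
| 176 / 184 | 1233, 1289 | 1261 | 1261 |
| 184 / 200 | 1289, 1401 | 1345 | 1345 |

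Thirteen of 14 match. The exception is off by 1009 − 985 = 24 days. The same check on all post-baseline boundaries in Tables 1–6 gives 54 matches out of 55.

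**Step 3: look for another rule that gives 985.** Target + 4 weeks is 953 + 28 = 981, the Table 1 bound for Week 136. Target + 8 weeks is 953 + 56 = 1009, which is what the formula row of Table 5, 1 + 7 × (X + 8), gives at X = 136. Every other boundary has the form 1 + 7k. For 985, (985 − 1) / 7 = 140.57, so no whole-week rule produces it.

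**Step 4: days affected.**

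| Day | Distance from Week 136 (953) | Distance from Week 152 (1065) |
|---|---|---|
| 986 | 33 | 79 |
| 1002 | 49 | 63 |
| 1008 | 55 | 57 |
| 1009 | 56 | 56 |
| 1010 | 57 | 55 |

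- Strictly nearer Week 136: days 986–1008, which is 1008 − 986 + 1 = 23 days. 23 / 112 = 20.5%.
- Counting day 1009, a tie that the tables elsewhere give to the earlier window: 24 days. 24 / 112 = 21.4%.
- A visit at nominal Week 144 may fall on days 1002–1016 (15 days). Seven of these are strictly nearer Week 136, or eight with the tie.
- A Week 136 sample within tolerance falls on days 946–960, and a Week 152 sample on days 1058–1072. Neither range touches days 986–1009.

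**The case against.** The SAP never states a midpoint rule. It asks for windows around a target that do not overlap and lose no data, and the printed rows meet that. This stands as a matter of wording: the rule is inferred from the other rows. The Week 0 / Week 8 boundary is not a midpoint either (day 1, where the midpoint of days 1 and 57 is 29), but it separates baseline from follow-up, so the pattern claimed here is for post-baseline windows only. With 54 of 55 of those boundaries at the midpoint, including the other 16-week gaps in the same table, and no reason given for the exception, a slip is the only reading the documents support.

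Several points limit the consequences, and they stand.

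- Nothing in the documents shows that any patient has a value on days 986–1009.
- A patient with on-schedule samples at both visits is summarised identically under either cut, because the value nearest the target is used.
- A Week 136 sample would have to be 33 days late to reach day 986, which is 26 days beyond tolerance.
- The correction does not give every EoT value a place. With samples on days 953 and 1000, both are shown now, at Weeks 136 and 152. After the fix both fall in Week 136, day 953 is used, and the day 1000 value leaves the by-visit table. It can still serve as the final observation under SAP Section 6.2, which does not depend on these windows.
- An EoT value on days 1010–1057 would still be labelled Week 152. That follows from sending early termination visits through the windows, not from this bound.

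**Conclusion.** The Week 136 upper bound and the Week 152 lower bound in Table 5 are wrong by 24 days against the pattern of every other post-baseline row. Followed as written, the table assigns hs-CRP values on days 986–1008 to the more distant visit. If EoT dates were spread evenly over the 112 days between the targets (an assumption, since the documents give no distribution), about one in five EoT values in that interval would be labelled with the wrong week.

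The effect is confined to the number of observations and the descriptive summary of hs-CRP change at Weeks 136 and 152, and it arises only if samples fall in the affected range. No hypothesis is tested, the primary objective is safety, and no other endpoint uses this table. It is a minor point, but clear-cut.

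**What to change.** In SAP Table 5, change the Week 136 upper bound from 985 to 1009 and the Week 152 lower bound from 986 to 1010. The rows become 926 / 953 / 1009 and 1010 / 1065 / 1093. The windows remain contiguous and non-overlapping, no value is left without a window, and no other row changes. Make the same change in the window program. A sentence in Section 6.4 stating that boundaries are midpoints of adjacent post-baseline targets, with the midpoint day in the earlier window, would make the rule checkable. The cost is two numbers and, optionally, that sentence.
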